## **8.7 Efficacy Analysis**

### **8.7.1 Primary Efficacy Endpoint**

The primary efficacy endpoint is defined as the proportion of patients achieving  $\geq 3$ -point improvement from baseline with respect to the weekly mean of the daily 24-hour Worst Itching Intensity NRS at Week 12 (Days 79 to 85) of the Double-blind Treatment Period.

The weekly mean of the 24-hour Worst Itching Intensity NRS score will be defined as the sum of the daily Worst Itching Intensity NRS scores reported during a specific week during the Double-blind Treatment Period (eg, Days 2 to 8, Days 9 to 15, Days 16 to 22, ... Days 79 to 85) divided by the number of days with nonmissing scores for that week. If the daily worst itching score is missing for  $>3$  days during a specific week, the corresponding weekly mean worst itching score will be set to missing. The baseline score will be defined as the average of the daily 24-hour Worst Itching Intensity NRS scores collected over the Run-in Period, including pre-randomization assessments collected on Day 1.

In the primary efficacy analysis, missing NRS data will be imputed using a multiple imputation (MI) approach, assuming that patients who discontinue double-blind treatment early would have similar Worst Itching Intensity NRS scores as other patients in their respective treatment arm that have complete data:

- Intermittent missing NRS scores will first be imputed using the Markov Chain Monte Carlo (MCMC) method implemented with the SAS MI procedure, which is appropriate for non-monotonic missing data.
- NRS scores missing after patients discontinue study drug early will then be multiply imputed with the SAS MI procedure using a method appropriate for

monotone missingness (eg, regression statement). Details on the MI procedure can be found in [Appendix 14.6](#).

- The proportion of patients who have an improvement from baseline with respect to the weekly mean of the daily 24-hour Worst Itching Intensity NRS score  $\geq 3$  points will be calculated for each imputed dataset. Differences between CR845 0.5 mcg/kg and placebo with respect to the primary endpoint will be compared using a logistic regression model containing terms for treatment group, baseline NRS score, use of prior anti-itch medication, presence of specific medical conditions, and country/region.
- Results of the logistic regression on the multiply imputed data sets will be summarized by the SAS MIANALYZE procedure.

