### 8.7.2 Secondary Efficacy Endpoints

The secondary efficacy endpoints are the:

- Proportion of patients achieving  $\geq 4$ -point improvement from baseline with respect to the weekly mean of the daily 24-hour Worst Itching Intensity NRS at Week 12 (Day 79 to 85) of the Double-blind Treatment Period;
- Proportion of patients achieving  $\geq 3$ -point improvement from baseline with respect to the weekly mean of the daily 24-hour Worst Itching Intensity NRS at Week 8 of the Double-blind Treatment Period;
- Proportion of patients achieving  $\geq 3$ -point improvement from baseline with respect to the weekly mean of the daily 24-hour Worst Itching Intensity NRS at Week 4 of the Double-blind Treatment Period;

- 
- Proportion of patients achieving  $\geq 4$ -point improvement from baseline with respect to the weekly mean of the daily 24-hour Worst Itching Intensity NRS at Week 8 of the Double-blind Treatment Period;
  - Proportion of patients achieving  $\geq 4$ -point improvement from baseline with respect to the weekly mean of the daily 24-hour Worst Itching Intensity NRS at Week 4 of the Double-blind Treatment Period;
  - Change from baseline in itch-related quality of life at the end of Week 12 of the Double-blind Treatment Period, as assessed by the Skindex-10 Scale total score;
  - Change from baseline in itch-related quality of life at the end of Week 12 of the Double-blind Treatment Period, as assessed by the 5-D Itch Scale total score.

The proportion of patients achieving  $\geq 4$ -point improvement from baseline at Week 12 of the Double-blind Treatment Period, the proportion of patients achieving  $\geq 3$ -point improvement from baseline at Week 8 and Week 4, and the proportion of patients achieving  $\geq 4$ -point improvement from baseline at Week 8 and Week 4 with respect to the weekly mean of the daily 24-hour Worst Itching Intensity NRS will be analyzed following a methodology similar to the one employed for the primary analysis of the primary endpoint.

The Skindex-10 Scale total score and the 5-D Itch Scale total score change from baseline at Week 12 will be analyzed using an analysis of covariance (ANCOVA) model that will contain treatment as fixed effect, with baseline score, region, and the randomization stratification variables as covariates. The baseline 5-D total score and the Skindex-10 total score will be defined as the value collected on Day 1, prior to randomization.

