For each domain in each questionnaire, missing values at Week 12 will be imputed using an MI approach, assuming that patients who discontinue double-blind treatment early would have similar domain scores as other patients in their respective treatment arm that have complete data:

- Intermittent missing scores will first be imputed using the Markov Chain Monte Carlo (MCMC) method implemented with the SAS MI procedure, which is appropriate for non-monotonic missing data;
- The monotone missing values will then be multiply imputed with the SAS MI procedure using the monotone regression method;
- For each stage, MI will be performed within treatment group with covariates for baseline score, region, both randomization stratification factors, and all non-missing visit scores for each domain of the questionnaire;
- For each questionnaire, the total score at each visit will be computed from the domain scores for each imputed dataset;

- 
- The ANCOVA analysis described above will be implemented for each imputed dataset. Results of the ANCOVA on the multiply imputed data sets will be summarized by the SAS MIANALYZE procedure.

The LS means, standard errors, 95% CIs, and differences between treatment groups reported with LS means, standard errors, and 95% CIs derived from the ANCOVA on the imputed datasets will be reported.

Additionally, a sensitivity analysis of the 5D Itch scale and the Skindex-10 scale will be performed to describe the time course of the treatment response over the 12-week treatment period using a mixed effects model with repeated measures (MMRM). The model will contain treatment, week, and treatment-by-week interaction as fixed effects; baseline score, prior anti-itch medication usage, presence of specific medical conditions, and country/region as covariates. Repeated measures will include values collected at the end of Weeks 4, 8, 10, and 12 (end of treatment). It is important to note that, in HD patients, the study drug administered during the last dialysis of a particular week is not cleared until the first dialysis of the next week. Therefore, measurements that would reflect treatment effect at the end of a specific week (eg. Week 4) will actually be collected during the first day of the next week (eg, Week 5).

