## 14.6 Statistical Appendix

This appendix provides further details related to the treatment of missing data for the primary and sensitivity analyses of the primary endpoint.

For multiple imputations and other instances where random seeds are required, the values used (in order) are:

8392857  
2985729  
1843255  
9086284  
5547484  
8017456  
9597295  
2252256  
4821871  
9852467  
5126715  
3232132  
9841654  
3645284  
1587345

Note that not all seeds may be required in programming the multiple imputations. If additional seeds are needed, they will be chosen by adding 1 to each of the values above, again using them in order.

The number of imputations for the multiple imputations will be 20.

For the primary analysis, a multi-stage process will be applied:

Stage 1: Subjects will have their 11-point NRS scores imputed. First, using all visits, intermittent missing data will be imputed using the Markov Chain Monte Carlo (MCMC) method implemented with the SAS MI procedure; data imputed following subject discontinuation via this process will be censored out of the resulting dataset so that only intermittent missing data is imputed via this method. Second, monotone missing data will be imputed following subject discontinuation using SAS proc MI. For each stage, MI will be performed within treatment group with covariates for baseline NRS score, use of prior anti-itch medication, and presence of select medical conditions. Should convergence issues occur due to small cell size for the one or both of the categorical covariates at either stage, the appropriate covariate(s) will be removed from the model.

Stage 2: Using the resulting complete datasets, the change from baseline with respect to the 11-point NRS will be calculated; patients will be categorized as responder if they have a 3-point (or greater) improvement over baseline. Week 12 values will serve as the primary timepoint. The 20 MI runs will be analyzed independently using a logistic

---

model and the results combined using SAS proc MIANALYZE. Logistic model covariates will include treatment, baseline NRS score, use of prior anti-itch medication, and presence of select medical conditions. As with the MI, should convergence issues occur due to small cell sizes, the appropriate categorical covariate(s) will be dropped as necessary.

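### Appendix 14.6 leaves region out of the NRS imputation and out of its logistic model, while Section 8.7.1 and the quality-of-life imputation include it (minor)

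*Protocol*

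**What the plan says.** Section 8.7.1 describes a two-step imputation (MCMC for intermittent gaps, then a monotone method after discontinuation) and sends the reader to Appendix 14.6 for the details. It specifies the analysis as a "logistic regression model containing terms for treatment group, baseline NRS score, use of prior anti-itch medication, presence of specific medical conditions, and country/region". The synopsis gives the same terms.

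Appendix 14.6, Stage 1, gives the covariates for both imputation steps: "MI will be performed within treatment group with covariates for baseline NRS score, use of prior anti-itch medication, and presence of select medical conditions". Stage 2 then lists the model fitted to the completed data: "Logistic model covariates will include treatment, baseline NRS score, use of prior anti-itch medication, and presence of select medical conditions". Neither list contains region.

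For Skindex-10 and 5-D, Section 8.7.2 also imputes within arm by MCMC and then monotone regression, but with "covariates for baseline score, region, both randomization stratification factors, and all non-missing visit scores for each domain of the questionnaire". The ANCOVA there is fitted "with baseline score, region, and the randomization stratification variables as covariates", so imputation and analysis models agree on region for those two endpoints.

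**The concern.** An imputation model should normally contain at least the covariates of the analysis model. If it does not, missing values are filled in as though the omitted covariate carried no further information, and are then analysed with that covariate in the model. If region is related both to leaving treatment and to later itch, beyond what the imputation already conditions on, the imputed response rates are biased. The treatment difference is biased when that pattern differs between arms.

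This imputation supplies the Week 12 outcome of patients who stop early: Table 2 schedules no NRS at the follow-up visit. Section 8.7.2 applies similar methods to the five NRS responder endpoints among the seven secondary endpoints, and Sensitivities 2 and 3 also use multiple imputation.

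The second problem is that the main text and the appendix specify different logistic models for the primary test.

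**Working it through.** **1. The covariate lists side by side**

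| Place in the protocol | Step | Region? |
|---|---|---|
| Synopsis; 8.7.1 | Primary logistic model | Yes |
| 14.6, Stage 2 | Primary logistic model | No |
| 14.6, Stage 1 | NRS imputation, both steps | No |
| 8.7.2 | Skindex-10 and 5-D imputation | Yes |
| 8.7.2 | Skindex-10 and 5-D ANCOVA | Yes |

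Within 14.6 the imputation and analysis models match. The mismatch arises when Stage 1 is read with 8.7.1.

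**2. The plan's own power figure**

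Section 8.2 has n = 175 per arm, response rates of 30% and 50%, two-sided 5%, continuity-corrected. With mean rate 0.40:

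z = [0.20 − 1/175 − 1.96 × √(2 × 0.40 × 0.60/175)] / √[(0.30 × 0.70 + 0.50 × 0.50)/175]
= (0.2000 − 0.0057 − 0.1026) / 0.0513 = 1.79, so power is 96.3% against 96% stated.

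The rest of Table 4 also reproduces within rounding (92.0%, 84.8% and 79.9% against 92%, 84% and 79%), and Table 5 reproduces exactly. These tables use neither covariates nor missing data, so the point does not change them. The denominator, 5.1 percentage points, is the standard error used as a yardstick below.

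**3. Size of the effect**

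The protocol gives no dropout rate, number of regions or regional effect. All inputs in this step are assumptions.

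*Simulation A, response proportions.* 175 per arm; 40% of patients in a region improving 1 point more by Week 12; 250 trials; 5 imputations; sequential regression within arm on baseline and up to three previous weekly changes.

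- Dropout of 25% in that region and 5% elsewhere, in both arms. Full data: 48.3% − 29.0% = 19.3 points. Imputed without region: 47.4% − 28.1% = 19.3. Each arm is 0.9 points low and the difference is unchanged. Imputed with region: 48.3% and 28.8%.
- The same pattern in the active arm only, placebo 10% everywhere. Bias of the difference is −0.9 points without region (Monte Carlo standard error 0.1) and −0.1 with region. Relative to the yardstick: 0.9/5.1 = 0.18 standard errors.

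*Simulation B, logistic model with region.* 175 per arm; three regions (50/25/25%) with itch improvement shifted by 0, +s and −s points; monotone regression within arm on all previous weekly scores; 10 imputations; 150 trials per row. Where dropout depends on region, the rate is multiplied by 1, 1.8 and 0.2, so 15% becomes 15/27/3% and 25% becomes 25/45/5%.

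| Shift s | Average dropout | Depends on region? | OR, region in imputation | OR, region left out | Change |
|---|---|---|---|---|---|
| 0 | 15% | No | 2.624 | 2.629 | +0.2% |
| 0.75 | 15% | No | 2.669 | 2.638 | −1.2% |
| 1.5 | 15% | No | 2.736 | 2.698 | −1.4% |
| 0.75 | 15% | Yes | 2.524 | 2.516 | −0.3% |
| 1.5 | 25% | Yes | 2.589 | 2.530 | −2.3% |
| 0.75, plus treatment-by-region difference | 25% | Yes | 2.702 | 2.629 | −2.7% |

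Power with and without region differed by at most about 1 point in every row. The mean absolute difference in log odds ratio per trial was 0.025 to 0.052, against standard errors of 0.25 to 0.28; 0.025 is what occurs with no regional effect at all.

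**The case against.** **The premise is contested inside the protocol.** A reader might infer that the primary analysis model plainly contains region and the imputation simply fails to match it. Stage 2 of 14.6 does not support that: it drops region too, and the protocol does not say whether 8.7.1 or 14.6 prevails. This stands. The mismatch is conditional on 8.7.1 governing, and the contradiction over the logistic model is part of the point.

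**Regional differences are not ignored.** A reader might also infer that a dropout's later scores are drawn as if regions did not differ. That is too strong. Baseline NRS is in the model, and the appendix says "First, using all visits, intermittent missing data will be imputed using the Markov Chain Monte Carlo (MCMC) method". Monotone regression ordinarily conditions on earlier scores as well, although 14.6 does not list them as 8.7.2 does. A patient's own history carries much of any regional difference, least so for early dropouts. Missing-at-random fails only if region adds information beyond that history. Both simulations condition on earlier scores, so their figures show what remains.

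**The sensitivity analyses are harsher.** Sensitivity 1 counts early discontinuations as nonresponders. Sensitivity 2 imputes adverse-event dropouts from baseline values. The tipping-point analysis shifts active-arm scores by up to 5 points. These limit the risk to the conclusion but do not correct the primary model.

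**The simulations are not the planned analysis.** The plan uses 20 imputations. Simulation A compares raw proportions; only Simulation B fits a logistic model containing region. They indicate order of magnitude and no more.

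**Conclusion.** The point holds as a minor specification flaw. Appendix 14.6 fixes covariate lists without region at both stages. The main text puts region in the primary logistic model, and the parallel quality-of-life imputation includes it. The protocol gives no reason for the difference. This is text that conflicts, not detail left to the SAP, although Section 8.1 lets the SAP prevail and it should be checked there.

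Under the assumed inputs, the largest effect found was about 0.9 percentage points in the difference, or 3% on the odds ratio, both towards no effect. A conclusion that the primary result is threatened, or tilted in favour of CR845, is not supported. The sizes rest on the assumed regional shifts (up to 1.5 points), the assumed dropout, and conditioning on earlier weekly scores in the monotone step.

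**What to change.** In Appendix 14.6:

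- Add region to the covariates of both Stage 1 steps, grouped as in the analysis model, with a prespecified rule for pooling sparse regions.
- Carry region into the missing-at-random imputation steps of Sensitivities 2 and 3. The adverse-event component of Sensitivity 2 draws from baseline values and is not affected.
- Make the Stage 2 logistic covariates agree with Section 8.7.1.
- Reword the rule for dropping covariates on non-convergence. It now refers only to the two existing categorical covariates and would not reach region.

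The cost is a few phrases and one covariate in the code, settled before unblinding. The downside is slightly smaller cells. This matters mainly if the sample size is increased, because the appendix then imputes the interim and post-interim cohorts separately: about half of 350 is 175 patients, or roughly 87 per arm, in the interim cohort. The pooling rule is there for that case.
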